17.1.4. SENSITIVITY ANALYSIS OF PRIMARY EFFICACY VARIABLE(S)

As sensitivity analyses, the primary efficacy analysis will be repeated on the ITT/Safety analysis sets.

17.2. SECONDARY EFFICACY

The secondary efficacy analyses will be performed for the EFF and ITT/Safety analysis set.

17.2.1. SECONDARY EFFICACY VARIABLES & DERIVATIONS

17.2.1.1. Unconfirmed objective response (uORR)

uORR is a unconfirmed best overall response (uBOR) of PR or CR. In the situation of lack of RECIST evaluation data (cohort 4 only), unconfirmed objective response as per GCIG criteria will be done using CA-125 levels.

Patients will be scored as having attained a CA-125 unconfirmed response if they meet the GCIG-Rustin-modified criteria which require that there is at least a 50% reduction in CA-125 levels from a pre-treatment sample. This will be used during the futility monitoring analyses.

Document: T:\sas\Debiopharm\Debio_1143\CZA60507\Biostatistics\Documentation\SAP\SAP Text\V5

Author: XXXXXXXXXX Version Number: 5.0
Version Date: 19APR2022

Template No.: CS_TP_BS016 Revision 5
Effective Date: 01Apr2018

Reference: CS_WI_BS005

17.2.1.2. Unconfirmed best overall response (uBOR)

The uBOR will be defined as the best response across all post-baseline tumour assessments that occur before the start of a new anti-neoplastic therapy. For example, a subject who has SD at the first assessment, PR at the second assessment, and PD at the last assessment has a BOR of PR. The order to obtain the BOR is the following: CR, PR, SD, PD, Not Evaluable (NE).

If a subject has no post-baseline tumour assessments, BOR will be NE.

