## 8.2. Study assessments

### 8.2.1. Efficacy

Tumors will be assessed according to either RECIST version 1.1 guidelines by CT scan or MRI imaging of the target/non target lesions (38), and/or GCIG criteria using the serum marker CA-125 for Cohort 4, if applicable.(39)

CT scan and MRI will be performed at screening, then every 8 weeks ( $\pm$  1-week tolerance window) during the first 10 cycles, then every 12 weeks ( $\pm$  1 week) from Cycle 13 until symptomatic PD or confirmed iRECIST PD or start of any new cancer treatment or end-of-life care or end of the Main study period, whichever occurs first. For patients who exceptionally continue study treatment after completion of 13 cycles, tumor response assessments will continue at 12-week intervals ( $\pm$  1 week window) until the end of the Main study period, and thereafter at the frequency of local institutional care practice until PD, start of any new anticancer therapy, death or EOT.

Imaging will be performed as per site standard but whenever possible using contrast agent at screening and during treatment

CA-125 dosages will be performed at screening exclusively in patients included in Cohort 4. In case of abnormally elevated levels before treatment start, these dosages will be repeated on Day 1 of each subsequent cycle.

In case of response, efficacy assessments will be repeated 4 weeks later after first documentation (+ 1-week tolerance window). All patients will have an efficacy assessment (CT scan/MRI or serum CA-125 dosage) at the time of disease progression and/or treatment discontinuation, whichever occurs first.

As an exploratory analysis, tumor response will also be assessed using the iRECIST criteria (novel modified RECIST v1.1 guideline for immunotherapeutics).(40) These exploratory analyses will be described in the SAP.

Patients with asymptomatic, but radiologically observed unconfirmed PD as per iRECIST, may continue the study treatment, upon both the Investigator's request and the Sponsor's agreement, until PD is confirmed as per iRECIST or symptoms occurs or Investigator/patient decision to withdraw treatment, whichever occurs first.

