#### **11.4.1. Derived parameters and endpoints**

##### **11.4.1.1. Efficacy**

Patients without any new anticancer therapy or PD will be assessed for anti-tumor efficacy every 8 weeks (±1 week) during the first 10 cycles and then every 12 weeks (± 1 week) from Cycle 13 onwards until PD occurs or start of a new cancer treatment or end-of-life-care or until the end of the Main study period whichever occurs first. For patients who continue study treatment after the Main study period, tumor

response assessments will continue at the frequency of local institutional care practice until PD, start of any new anti-cancer therapy, death or EOT, whichever occurs first.

Response according to RECIST version 1.1 (38) or GCIG criteria (39) (Cohort 4 for RECIST non-evaluable patients) will be assessed in the efficacy and ITT populations. CR and PR must be demonstrated by objective tumor assessment (CT scan/MRI or CA-125 dosage) and confirmed 4 weeks later. All patients will have a CT scan/MRI or CA-125 dosage at the time of PD. Tumor response will also be assessed by using the novel modified RECIST v1.1 guideline for immunotherapeutics, iRECIST.(40) These exploratory analyses using iRECIST guideline will be presented in detail in the SAP.

In case of premature discontinuation with SD at the EOS visit, this SD will be included in the derivation of efficacy parameters only if the assessment has been performed at least 35 days after treatment start.

The start of a systemic new anti-cancer therapy without prior disease progression could potentially impact the tumor activity observed, hence potentially biasing the evaluation of Debio 1143 anti-tumor activity. As a consequence, no further efficacy data will be collected after the start of any new anti-cancer treatment, except for OS, at least until study data cut-off.

The confirmed response will be used in the primary ORR analysis while a secondary analysis will be performed using the unconfirmed response.

- **Objective response** is derived as any PR or CR recorded after the start of study treatment until disease progression/recurrence is documented, a new systemic anti-cancer therapy is started or analysis cut-off, whichever occurs first.
- **BOR** is the best response (CR, PR, stable disease or disease progression) recorded after the start of study treatment until disease progression/recurrence is documented, a new systemic anti-cancer therapy is started or analysis cut-off, whichever occurs first.

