7.4. UNSCHEDULED VISITS

In general, for by-visit summaries, data recorded at the nominal visit will be presented (including early termination visit like “end of treatment” or “end of study”). Unscheduled measurements will not be included in by-visit summaries but will contribute to the best/ worst case value where required (e.g. shift table). Listings will include both scheduled and unscheduled data.

All tumour assessment and/or CA-125 data from both scheduled and unscheduled visits will be included in the analyses described in section 17 of this SAP.

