17.2.1.4. Disease control

Disease control is derived as an uBOR of CR, PR or SD recorded at any point during the study.

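### SAP 17.2.1.2 lets a response seen after RECIST progression count towards unconfirmed best response, whereas protocol 11.4.1.1 closes the window at progression, and SAP 4.3 does not declare the change

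*SAP*

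**What the plan says.** **Protocol.** Section 11.4.1.1 defines objective response as "any PR or CR recorded after the start of study treatment until disease progression/recurrence is documented". The best overall response bullet has the same limit: "until disease progression/recurrence is documented, a new systemic anti-cancer therapy is started or analysis cut-off, whichever occurs first". The disease control bullet in that section asks only for a CR, PR or stable disease during the study and does not mention progression.

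**SAP.** Section 17.2.1.2 takes the "best response across all post-baseline tumour assessments that occur before the start of a new anti-neoplastic therapy" and ranks CR, PR and SD ahead of PD. Neither progression nor analysis cut-off closes the window. Two other definitions rest on it. Section 17.2.1.1 says "uORR is a unconfirmed best overall response (uBOR) of PR or CR", and section 17.2.1.4 says "Disease control is derived as an uBOR of CR, PR or SD recorded at any point during the study". Section 17.2.1.6 computes duration of response for every patient whose uBOR is CR or PR. SAP 4.3, which lists changes from the protocol, does not mention the response window.

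**Scans after progression.** Protocol 8.2.1 says "Patients with asymptomatic, but radiologically observed unconfirmed PD as per iRECIST, may continue the study treatment", subject to an investigator request and sponsor agreement. Protocol 8.3.2.1 also allows continuation where pseudoprogression is suspected. Imaging runs to symptomatic or confirmed iRECIST progression, not to the first RECIST progression.

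**The concern.** Two programmers, one working from the protocol and one from the SAP, would classify the same patient differently. Under RECIST v1.1, as summarised in protocol Appendix C, a patient who has met the criteria for progression cannot then be given CR, PR or SD. Responses after apparent progression belong to iRECIST, which is exploratory in this trial.

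The affected quantity also drives decisions. The binding futility looks count unconfirmed responses, and one patient decides each look: 0 against 1 of 8, and 1 against 2 of 11. At the reporting stage the same window feeds the uBOR tables and plots, disease control and duration of response.

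**Working it through.** **1. The two rules applied to the same sequences**

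| Sequence of assessments | SAP 17.2.1.2 as written | Protocol 11.4.1.1 |
|---|---|---|
| SD, PR, PD (the SAP's own example) | PR | PR |
| PD, PR | PR | PD |
| SD, PD, PR | PR | SD |
| PD, SD | SD | PD |

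The SAP's example gives the same answer under both rules, so it does not settle the question. The other three rows differ.

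**2. Duration of response**

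SAP 17.2.1.6 uses (first documented progression or death − initial response + 1) / 30.4375. For illustration, take progression at day 56 and PR at day 112:

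56 − 112 + 1 = −55 days, or −55 / 30.4375 = −1.8 months.

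The formula works only if response comes before progression. In section 17.2.1.5 the same patient has a PFS event at day 56, before the response is recorded.

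**3. The plan's futility boundaries**

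Inputs from protocol 11.6.4.3 and SAP 5.3: prior Beta(0.5, 0.5), futility reference rate 0.05, threshold 0.2. The posterior is Beta(0.5 + r, 0.5 + n − r), and a cohort stops if P(θ ≤ 0.05) > 0.2.

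| r/n | P(θ ≤ 0.05) | Action |
|---|---|---|
| 0/8 | 0.643 | stop |
| 1/8 | 0.149 | continue |
| 1/11 | 0.224 | stop |
| 2/11 | 0.042 | continue |

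The stated boundaries (0 of 8, and 1 or fewer of 11) reproduce. They do not change under the fix; only who counts as a responder changes.

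**4. Sensitivity of stopping to the window**

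P(stop) = P(0 of 8) + P(1 of 8) × P(0 of 3) = (1 − p)^8 + 8p(1 − p)^10.

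Let q be the share of RECIST non-responders with a countable response after progression. The documents give no value for q, so 0%, 2% and 5% are assumptions. With a true RECIST rate of 5%, p = 0.05 + 0.95q.

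| q (assumed) | p | P(0 of 8) | P(stop) |
|---|---|---|---|
| 0% | 0.05 | 0.663 | 0.663 + 0.240 = 0.903 |
| 2% | 0.069 | 0.564 | 0.564 + 0.270 = 0.834 |
| 5% | 0.0975 | 0.440 | 0.440 + 0.280 = 0.720 |

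**The case against.** The best defence is that the intent is clear from other text. SAP 17.3.1.1 moves patients to iRECIST follow-up after their first RECIST progression. Section 17.3.2 lists separate RECIST and iRECIST overall-response forms. The RECIST spider plot in 17.2.3.2 stops at progression, while its iRECIST counterpart runs to confirmed progression. The futility count is of responses by RECIST v1.1 or GCIG, and Appendix C excludes a RECIST response after progression. SAP 7.4 ("All tumour assessment and/or CA-125 data from both scheduled and unscheduled visits will be included in the analyses described in section 17") sits under unscheduled visits and concerns which visits count, not when the window closes. A careful programmer might therefore apply the stop anyway, which is the 0% row. This stands as evidence of intent, but none of it is carried into the uBOR sentence, which is the operative rule.

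A reader might also infer three stronger things that the documents do not support.

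- **That the SAP's disease control definition contradicts the protocol's.** It does not, because the protocol's own bullet has no progression cut-off. The SAP inherits the gap through uBOR.
- **That the primary endpoint has the same fault.** Section 17.2.1.3 ties confirmed best response to RECIST 1.1 guidance, and its table turns PR followed by PD into SD or PD. What remains is smaller. No row begins with PD, and the footnote lets the confirming scan be a later one, so PR, PD, PR is not expressly excluded.
- **That futility decisions went wrong.** SAP 4.3 already refers to the futility of the Part B cohorts, and the modification history dates that statement to version 4.0 of July 2021. A looser count can only make stopping harder, so it cannot have caused those stops.

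The 2% and 5% figures are not estimates. They apply to all RECIST non-responders, although continuing past asymptomatic progression needs agreement patient by patient.

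**Conclusion.** The point holds as an undeclared difference between the SAP's uBOR window and the protocol's window for objective response and best overall response. Read literally, the SAP scores PD then PR as an unconfirmed RECIST responder and PD then SD as SD, and it allows a negative duration of response.

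The classification differences and the negative duration need no assumption beyond a patient having such a sequence. The documents do not show whether any patient does. The effect on futility stopping (0.903 falling to 0.834 or 0.720 at a true 5% rate) depends entirely on the assumed post-progression response rate, and is zero if the stop is applied in programming. With the Part B cohorts already described as futile, the practical gain is mainly correct reporting of uBOR, disease control and duration of response. That merits a correction, but it does not call the primary endpoint or the futility outcome into question.

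**What to change.** In SAP 17.2.1.2, limit the assessments used to those *up to and including the first documented RECIST v1.1 (or, where CA-125 is used, GCIG) progression, start of new systemic anti-cancer therapy or analysis cut-off, whichever occurs first*. Let 17.2.1.1, 17.2.1.4 and 17.2.1.6 use that window, state in 17.2.1.3 that it also applies to confirmed best response, and report later responses only under iRECIST best overall response. Because the protocol's disease control bullet is silent on progression, note in SAP 4.3 that the window is applied there too.

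If the wider window is intended, SAP 4.3 should declare and justify it, and the duration of response formula would then need its own repair.

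The cost is one sentence, a few cross-references and a check of the derivation programs. No new data are needed. The unconfirmed response and disease control rates can only stay the same or fall.

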17.2.1.3. Confirmed best overall response (cBOR)

The cBOR will also be analysed. In this case, CR and PR need to be confirmed at a subsequent assessment, at least 4 weeks after the initial overall response assessment of CR/PR and before the start of a new anti-neoplastic therapy or administration of non-permitted concomitant medications. cBOR will be derived as described in the RECIST 1.1 guidance.

Overall response first time point	Overall response subsequent time point*	cBOR
CR	CR	CR
CR	PR	SD, PD or PR ^a
CR	SD	SD, if minimum criteria for SD duration met, otherwise PD
CR	PD	SD, if minimum criteria for SD duration met, otherwise PD
CR	NE	SD, if minimum criteria for SD duration met, otherwise NE
PR	CR	PR
PR	PR	PR
PR	SD	SD
PR	PD	SD, if minimum criteria for SD duration met, otherwise PD
PR	NE	SD, if minimum criteria for SD duration met, otherwise NE
NE	NE	NE

* Subsequent time point is not necessarily the direct subsequent scan (eg. PR-SD-PR will have PR as confirmed BOR)

^a If a CR is truly met at first time point, then any disease seen at a subsequent time point, even disease meeting PR criteria relative to baseline, makes the disease PD at that point (since disease must have reappeared after CR). Best response would depend on whether minimum duration for SD was met. However, sometimes ‘CR’ may be claimed when subsequent scans suggest small lesions were likely still present and in fact the patient had PR, not CR at the first time point. Under these circumstances, the original CR should be changed to PR and the best response is PR.

When SD is believed to be the best response, it must also be a minimum of 35 days after treatment day 1. If the

Document: T:\sas\Debiopharm\Debio_1143\CZA60507\Biostatistics\Documentation\SAP\SAP Text\5

Author: [REDACTED] Version Number: 5.0
Version Date: 19APR2022

Template No.: CS_TP_BS016 Revision 5
Effective Date: 01Apr2018

Reference: CS_WI_BS005

minimum time is not met, the subject’s best overall response depends on the subsequent assessments. For example, a subject who has SD at the first assessment, PD at the second assessment and does not meet the minimum duration for SD, will have a best overall response of PD. The same subject lost to follow-up after the first SD assessment would be considered NE for BOR.

17.2.1.4. Disease control

Disease control is derived as an uBOR of CR, PR or SD recorded at any point during the study.

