    - f. Immunosuppressive medication: within 2 weeks, with the exception of intranasal and inhaled corticosteroids or systemic corticosteroids at physiological/replacement doses, which should never exceed 10 mg/d prednisone, or an equivalent corticosteroid
  7. Measurable disease (Part B only) according to RECIST v1.1 or GCIG criteria in Cohort #4 (if applicable) and documented PD during or after prior PD-1/PD-L1 based therapy
  8. ECOG Performance Status = 0 or 1
  9. Adequate hematologic renal and hepatic function:
    - a. absolute neutrophil count (ANC)  $\geq 1.5 \times 10^9/L$ ,
    - b. platelets  $\geq 100 \times 10^9/L$ ,
    - c. hemoglobin  $\geq 9.0$  g/dL,
    - d. AST and ALT  $\leq 3 \times$  ULN ( $\leq 5 \times$  ULN if liver metastases are present),
    - e. total bilirubin  $\leq 1.5 \times$  ULN,
    - f. serum creatinine  $\leq 1.5 \times$  ULN,
    - g. serum albumin  $\geq 30$  g/L
  10. Available archived tumor samples for biomarker analysis obtained after prior PD-1/PD-L1 treatment failure or, if no archived tumor sample is available, patient must be suitable and willing to undergo a percutaneous or endoscopic biopsy without unacceptable major risks before starting study treatment.
  11. Participants with known central nervous system (CNS) and/or meningeal involvement will be eligible if they are clinically asymptomatic, have completed primary CNS therapy more than 4 weeks before treatment start (such as whole brain RT, stereotactic radiosurgery, or complete surgical resection), and have remained off steroids (including tapering doses) for at least 2 weeks
  12. Women of child-bearing potential (WOCBP):
    - a. Negative serum pregnancy test at screening;
    - b. Agreement to use highly effective contraception methods from study entry and for up to 5 months after the last day of study treatment
    - c. Agreement from her male partner to use contraception methods
  13. Male patients with WOCBP partners must agree to use highly effective contraception methods from study entry and for up to 5 months after the last day of study treatment

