#### 8.1.2. Secondary endpoints

Secondary endpoints for both study parts (unless otherwise specified) are:

- Incidence and severity of TEAEs and clinical laboratory abnormalities, according to NCI-CTCAE version 5.0 criteria
- Changes in vital signs: systolic/diastolic blood pressure, heart rate (both after at least 5 minutes of supine rest), temperature, and weight; ECG and ECOG-PS
- Incidence of premature treatment discontinuations and treatment modifications due to AEs and laboratory abnormalities (i.e., treatment compliance)
- Tumor response determined according to RECIST v1.1 and/or GCIG criteria (Cohort 4, if applicable):
  - Confirmed (Part A) and unconfirmed (Parts A and B) ORR
  - Disease control rate (DCR), defined as any response, partial or complete (PR or CR) + stable disease (SD)
  - Time-related endpoints as median time to response, median DOR, median PFS, PFS rate at 6, 12 and 18 months, median OS, OS rate at 12 months and 18 months (if data allow)

- PK parameters of Debio 1143 and Debio 1143-MET1 as defined in the available population PK model (36) and, if appropriate, post-hoc estimates of areas under the curve (AUCs),  $C_{max}$ , and  $C_{min}$ ; serum concentration versus time profiles of nivolumab and, if deemed appropriate, relevant nivolumab PK parameters derived from a population PK model. (37)

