3.2. SECONDARY ENDPOINTS

Secondary endpoints for both study parts (unless otherwise specified) are:

- Incidence and severity of treatment-emergent adverse events (TEAEs) and clinical laboratory abnormalities, according to National Cancer Institute-Common Terminology Criteria for Adverse Events NCI-CTCAE version 5.0 criteria
- Changes in vital signs: systolic/diastolic blood pressure, heart rate (both after at least 5 minutes of supine rest), temperature, and weight; electrocardiogram (ECG) and Eastern Cooperative Oncology Group Performance Status (ECOG-PS)
- Incidence of premature treatment discontinuations and treatment modifications due to TEAEs and laboratory abnormalities (i.e., treatment compliance)
- Tumor response determined according to RECIST v1.1 and/or GCIG criteria (Cohort 4, if applicable):
 - Confirmed (Part A) and unconfirmed (Parts A and B) ORR
 - Disease control rate (DCR), defined as any response, partial or complete (PR or CR) + stable disease (SD)
 - Time-related endpoints as median time to response, median duration of response (DOR), median progression-free survival (PFS), PFS rate every months, median overall survival (OS), OS rate at 12 months and 18 months (if data allow)
- PK parameters of Debio 1143 and Debio 1143-MET1 as defined in the available population PK disposition model and, if appropriate, post-hoc estimates of areas under the curve (AUCs), C_{max}, and C_{min}; serum concentration versus time profiles of nivolumab and, if deemed appropriate, relevant nivolumab PK parameters derived from a population PK model.

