17.1.1. PRIMARY EFFICACY VARIABLE & DERIVATION

The primary efficacy variable is confirmed ORR as per RECIST v1.1 and/or CGIG criteria (cohort 4, if applicable).

Confirmed objective response as per RECIST v1.1 is a confirmed best overall response (cBOR) of partial response (PR) or complete response (CR). The full derivation of confirmed BOR is included in Section 17.2.1.2.

In the situation of lack of RECIST evaluation data (cohort 4 only), confirmed objective response as per GCIG criteria will be done using CA-125 levels. Patients will be scored as having attained a CA-125 response if they meet the GCIG-Rustin-modified criteria which require that there is at least a 50% reduction in CA-125 levels from a pre-treatment sample. The response must be confirmed and maintained for at least 28 days. Patients can be evaluated according to CA-125 only if they have a pre-treatment sample that is at least twice the upper limit of normal and within 2 weeks prior to starting treatment.

Document: T:\sas\Debiopharm\Debio_1143\CZA60507\Biostatistics\Documentation\SAP\SAP Text\V5

Author: [REDACTED] Version Number: 5.0
Version Date: 19APR2022

Template No.: CS_TP_BS016 Revision 5
Effective Date: 01Apr2018

Reference: CS_WI_BS005

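### SAP disease control has no CA-125 route, so a Cohort 4 patient who responds by CA-125 alone counts in the ORR but not in the DCR

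*SAP*

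**What the plan says.** The endpoint is stated alike in both documents. Protocol 8.1.2 has "Disease control rate (DCR), defined as any response, partial or complete (PR or CR) + stable disease (SD"), and SAP 3.2 repeats it. In both, DCR sits under a common heading; the SAP's is "Tumor response determined according to RECIST v1.1 and/or GCIG criteria (Cohort 4, if applicable").

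Patients followed by CA-125 alone are expected. Inclusion criterion 7 reads "Measurable disease (Part B only) according to RECIST v1.1 or GCIG criteria in Cohort #4". Protocol 8.2.1.2 provides monthly CA-125 for Cohort 4 patients without RECIST-measurable disease, and SAP 6.5 accepts a post-baseline CA-125 value for entry to the efficacy set.

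Where RECIST data are lacking in Cohort 4, SAP 17.1.1 says "confirmed objective response as per GCIG criteria will be done using CA-125 levels" and 17.2.1.1 says "unconfirmed objective response as per GCIG criteria will be done using CA-125 levels". SAP 17.2.1.5 (PFS) and 17.2.1.6 (duration of response) also have a CA-125 branch.

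Disease control (17.2.1.4) has only this: "Disease control is derived as an uBOR of CR, PR or SD recorded at any point during the study". On the uBOR scale, 17.2.1.2 says "The order to obtain the BOR is the following: CR, PR, SD, PD, Not Evaluable (NE") and "If a subject has no post-baseline tumour assessments, BOR will be NE".

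**The concern.** If a patient counts as a responder, she should also count as having disease control: DCR is responders plus stable patients. Under the SAP as written, this fails for a Cohort 4 patient whose response is known only from CA-125. She enters the numerator of the primary endpoint, while her uBOR is NE or unassigned and she is left out of disease control.

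At stake is a secondary endpoint that is understated in Cohort 4 and could be reported below the ORR of the same cohort. The BOR tables of 17.2.3.2 would also show a primary-endpoint responder as not evaluable. SAP 4.3, which lists departures from the protocol, does not mention this one.

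**Working it through.** Neither document gives a DCR figure or assumption, so there is no stated number to reproduce. The check is of the rule.

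**1. CA-125 routes in the SAP.**

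| Measure | SAP section | CA-125 branch |
|---|---|---|
| Confirmed ORR | 17.1.1 | yes |
| Unconfirmed ORR | 17.2.1.1 | yes |
| PFS | 17.2.1.5 | yes |
| Duration of response | 17.2.1.6 | yes |
| Disease control | 17.2.1.4 | no |

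**2. Can uBOR take in a CA-125 response?** Its categories are CR, PR, SD, PD and NE. No section assigns a 50% fall in CA-125 to any of them. Sections 17.2.1.1 and 17.2.1.6 name CA-125 response as an alternative to a uBOR of CR or PR, not as a source of it.

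**3. Effect.** In a cohort of n patients, let r = RECIST CR or PR, s = RECIST SD and c = CA-125-only responders; the rest are PD or NE.

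- Unconfirmed ORR = (r + c)/n
- DCR under 17.2.1.4 = (r + s)/n
- DCR with CA-125 responses counted = (r + s + c)/n

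The understatement is c/n. Per patient it is 1/8 = 12.5, 1/11 = 9.1 and 1/15 = 6.7 percentage points. DCR is below unconfirmed ORR when r + s < r + c, that is, when s < c.

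| n | r | s | c | ORR | DCR, SAP | DCR, CA-125 counted |
|---|---|---|---|---|---|---|
| 11 | 0 | 0 | 1 | 9.1% | 0% | 9.1% |
| 15 | 1 | 2 | 3 | 26.7% | 20.0% | 40.0% |
| 15 | 1 | 4 | 3 | 26.7% | 33.3% | 53.3% |

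These mixes are assumed, to show the mechanism. Over every possible (r, s, c), DCR is below ORR in 70 of 165 configurations at n = 8, 161 of 364 at n = 11 and 372 of 816 at n = 15. These are counts of configurations, not probabilities. With CA-125 responses counted, the number is 0 at each n.

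**4. Final analysis.** SAP 17.2.3.1 limits the unconfirmed ORR analysis to futility monitoring, so the final comparison is confirmed ORR against DCR. With r′ ≤ r and c′ ≤ c the confirmed counts, DCR is below confirmed ORR when r + s < r′ + c′, that is, when c′ > s + (r − r′). This is harder to meet than s < c, but the cause is the same. The understatement of DCR stays c/n.

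**The case against.** **The protocol's own derivation has no CA-125 branch.** Protocol 11.4.1.1 derives disease control from CR, PR or SD, close to the SAP sentence. But it derives objective response from PR or CR in the same way, and says that CR and PR may be shown by CT/MRI or CA-125. If a CA-125 response satisfies that wording for ORR, it does so for disease control. The SAP supplied the missing branch for one and not the other.

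**Tumour assessment may include CA-125.** SAP 6.5 and protocol 11.4.1.1 use the term that way, while SAP 7.4 names the two separately. So calling uBOR imaging-based is an inference. The broader reading still gives no rule for placing a CA-125 result on the uBOR scale, so the gap remains.

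**The reach is small.** This stands. DCR is descriptive and has no decision rule, CA-125 values are summarised by visit (17.2.3.4), and the alternative spider plot (17.3.2) can show CA-125 response. SAP 4.3 also refers to the futility of the Part B cohorts. A cohort stopped at 0 of 8 had no CA-125 responder at that check. One stopped at 11 had at most one responder of any kind, and DCR below ORR then needs that one to be CA-125-only and no patient with SD.

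Three stronger readings are tempting, and the documents do not support them:

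- *CA-125 patients without progression are wrongly denied disease control.* Protocol 8.2.1.3 and Appendix C define CA-125 response and progression, but no CA-125 stable disease. Their status is unstated, not contradicted.
- *Part A has the same conflict.* The CA-125 route into ORR is for Cohort 4 only (17.1.1, 17.2.1.1), as is CA-125 collection (17.2.1.8), and the cohorts belong to Part B. Part A need not have measurable disease, so the handling of non-CR/non-PD deserves a line, but that is a separate, minor clarification.
- *Any patient with non-target disease and a falling CA-125 shows the conflict.* If she has serial CT, she may not count as lacking RECIST data, and the CA-125 route may then be closed for ORR too.

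**Conclusion.** The point holds for Cohort 4 patients whose response rests on CA-125 because RECIST data are lacking. For them, SAP 17.2.1.4 gives a result at odds with the endpoint definition in SAP 3.2 and protocol 8.1.2, and with the SAP's own ORR. This is a stated rule that misclassifies a patient, not merely missing detail.

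The total size depends on how many such responders there are, which the documents do not give. It is zero if every Cohort 4 responder has RECIST data. The conclusion assumes that 17.2.1.4 is programmed as written and that the ORR sections admit the patient through CA-125. The primary endpoint, the futility boundaries and the efficacy boundary are unaffected. The correction is worth making because it is cheap, not because a trial decision turns on it.

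**What to change.** Amend SAP 17.2.1.4 so that, for Cohort 4 patients lacking RECIST evaluation data, a GCIG CA-125 response counts as disease control, with the same trigger as 17.1.1 and 17.2.1.1. Show CA-125 responses as their own line in the BOR tables of 17.2.3.2, so that these patients do not appear only as NE.

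State whether CA-125 patients with neither response nor progression count as disease control. Alternatively, report DCR in RECIST-evaluable patients only, with its own denominator, and say so in SAP 3.2 and 4.3.

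Separately, add a line on how non-CR/non-PD is classed in non-measurable disease, including Part A, and on whether CT of non-target disease alone counts as RECIST evaluation data.

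The cost is SAP wording and a few lines of programming. No new data are needed: CA-125 is already repeated on Day 1 of each cycle when raised before treatment (protocol 8.2.2.5), and the CA-125 response and progression rules are already in the SAP.
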